6.3.2.2 Supplementary Analyses

The estimand for the first supplementary analysis will pursue a while on-treatment strategy. This will use the mITT population. The endpoint will be the change from baseline in the modified UMSARS score at the last measured time point. For subjects that stay on study, this will be the Week 48 visit. For subjects that discontinue early, the last on-treatment visit will be used as the endpoint. The population summary will be the difference between placebo and Verdiperstat treated subjects at their last visit. The summary will be computed using an Analysis of Covariance (ANCOVA), estimated by Restricted Maximum Likelihood (REML) that will include fixed effect factors for treatment group and randomization strata. Baseline modified UMSARS score will be used as a covariate.

The estimand for the second supplementary analysis will pursue a hypothetical strategy that estimates the effect of treatment in compliant subjects. The endpoint and population summary will be the same as used for the primary estimand. However, the population and handling of intercurrent events will be handled differently. The population will consist of subjects that are at least 80% compliant with the drug regimen and complete the Week 48 visit. In terms of intercurrent events, subjects that discontinue treatment, or are lost to follow-up, before Week 48 are not included in the analysis.

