9.4.2 Primary Endpoint(s)

The primary endpoint is the change from baseline in the modified UMSARS score measured at the Week 48 visit. The items in the modified UMSARS will contain the following Part I items: Speech, Cutting Food and Handling Utensils, Dressing, Hygiene, Walking and Urinary Function. The following Part II items will also be included: Arising from Chair, Posture, and Gait. In the analysis of all items, the response categories of 0 and 1 will be combined into a single category before summing the individual items to derive the modified UMSARS.

The primary estimand, for the primary endpoint, will pursue a hypothetical strategy of estimating the effect of BHV-3241 relative to placebo had all subjects stayed on treatment. Using the mITT population, the summary will be the difference between placebo and BHV-3241 treated subjects at the Week 48 visit. The summary will be computed using a Mixed Model for Repeated Measures (MMRM) that will include fixed effect factors for treatment group, randomization strata (MSA-C or MSA-P, Possible or Probable MSA diagnosis, and country), visit, and the treatment group by visit interaction. Baseline modified UMSARS score will enter the model as a covariate, and subject will be a random effect. Intercurrent events that lead to discontinuation, or lack of data, will be handled by only using the-on treatment data. MMRM-based estimates (i.e., least-squares mean [LSM] with corresponding SD and 95% CI) of values and changes from baseline will be presented by treatment group and week. In addition, the LSM difference in change from baseline between treatment groups (BHV-3241 – placebo) at Week 48 with corresponding SD, 95% CI, and p-value from MMRM will also be presented. Since the estimate is calculated using a likelihood-based approach, the analysis is based on a Missing at Random (MAR) assumption. Sensitivity analyses will include multiple imputation of missing data using a copy increment from reference method.

Observed values and changes from baseline in the modified UMSARS scores will also be summarized using descriptive statistics over time by treatment group during the Randomization Phase.

Details of these analyses are provided in the SAP.

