3.2.1 Primary Objective Estimand

The estimands corresponding to the primary objectives for this study are shown in Table 1.

Table 1: Primary Objective Estimands

Objective	To evaluate the efficacy of Verdiperstat, compared to placebo, as measured by a change from baseline in a modified UMSARS score at Week 48
Efficacy Endpoint	Change from baseline in a modified UMSARS score at Week 48
Summary	Using the mITT population:
	 Descriptive statistics for modified UMSARS score and change from baseline as a continuous variable by treatment group at each visit
	 Difference in mean change from baseline in modified UMSARS scores between treatment groups at week 48 estimated and tested using a mixed-effect model for repeated measures (MMRM)
Intercurrent	1) Main Analysis - Observed data only
Events	2) Supplementary Analysis 1 – While on-treatment strategy
	3) Supplementary Analysis 2 – Compliant subjects hypothetical strategy
	4) Sensitivity Analysis – Multiple imputation jump to reference and copy increment from reference
	5) Sensitivity Analysis – Observed data only using narrower visit window for Week 48
Objective	To assess the safety and tolerability of Verdiperstat, relative to placebo, in subjects with MSA
Safety Endpoint	Frequency of unique subjects with serious adverse events (SAEs), AEs leading to study drug discontinuation, AEs related to study drug, clinically significant ECG abnormalities, and clinically significant laboratory test abnormalities
Summary	Number and percentage of subjects with safety events and findings for the safety population
Intercurrent Events	Treatment policy strategy, i.e., no accounting for intercurrent event

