6.2.6.1 Study Therapy

Double-Blind Phase

For the double-blind phase, the extent of subject exposure (i.e., treatment duration) will be quantified as the number of days on study medication and measured from the time the subject received the first dose of study medication until the time the subject received the last dose of study medication. Treatment duration includes missed dose days; i.e., last dose date of double-blind randomized study medication – first dose date of double-blind randomized study medication + 1.

The extent of subject exposure (i.e., total days on study medication) will also be calculated for each subject by counting days where the number of tablets taken was > 0 (i.e., treatment duration – number of days a subject missed all doses of double-blind randomized study medication). If a subject took at least one dose of study medication on a study day, then the subject will be counted as having received study medication on that day.

Additionally, percent (%) compliance will be calculated as (total days on double-blind randomized study medication) / (treatment duration of double-blind randomized study medication) \times 100.

The number and percentage of subjects who had dose titrations during the double-blind phase will also be summarized by time point and dose.

Open-Label Extension Phase

For the OLE Phase, the extent of subject exposure (i.e., treatment duration) will be quantified as the number of days on study medication and measured from the time the subject received the first dose of study medication in the OLE Phase until the time the subject received the last dose, either at the end of the study or withdrawal from the OLE Phase. Treatment duration includes missed dose days, i.e., last dose date of OLE study medication – first dose date of OLE study medication + 1.

The extent of subject exposure (i.e., total days on study medication) during the OLE Phase will also be calculated for each subject by counting days where the number of tablets taken was > 0 (i.e., treatment duration – number of days a subject missed all doses of OLE study medication). If a subject took at least one dose of study medication on a study day, then the subject will be counted as having received study medication on that day.

Additionally, percent (%) compliance will be calculated as (total days on open-label Verdiperstat study medication) / (treatment duration of open-label Verdiperstat study medication) × 100.

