and concurrent treatments. Study dropout including dropouts and missed visits due to COVID-19 pandemic (and corresponding discontinuation of assessments) will be handled by a hypothetical strategy to estimate what the outcome would have been at the designated time point if all subjects were continued to be assessed.

d. The mean change from baseline between treatment and placebo on the primary endpoint will be compared at 48 weeks. A significant difference with an error rate of 5% will be required for success.

The summary will be computed using a Mixed Model for Repeated Measures (MMRM) that will include fixed effect factors for treatment group, randomization strata (i.e., disease subtype, diagnostic category, and country), visit, and the treatment group by visit interaction. Baseline modified UMSARS score and the baseline neurofilament level will enter the model as covariates, and subject will be a random effect. Repeated measurements are made on each subject. The covariance structure for within subject error ("R" matrix in SAS proc mixed) will be initially specified as unstructured. If the model fails to converge, then a Huynh-Feldt structure may be used, followed by an AR(1) structure. Error degrees of freedom will be calculated using Kenward-Roger approximation if an unstructured covariance structure fits appropriately; otherwise, a sandwich estimator will be utilized to estimate the covariance structure and degrees of freedom will be calculated using the between-within method.

MMRM-based estimates (i.e., least-squares mean [LSM] with corresponding SD and 95% CI) of values and changes from baseline will be presented by treatment group and week. In addition, the LSM difference in change from baseline between treatment groups (Verdiperstat – placebo) at Week 48 with corresponding SD, 95% CI, and p-value from MMRM will be presented.

Observed values and changes from baseline in the modified UMSARS score will be summarized using descriptive statistics over time by treatment group.

Effect sizes (Cohen's D) of the individual items within the modified UMSARS will also be summarized to assess the strength of the effect of Verdiperstat on each individual item.

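### Supplementary Analysis 2 is called a hypothetical strategy but is a per-protocol completers comparison, which is biased if outcome-related drop-out differs between arms

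*SAP*

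**What the plan says.** SAP 6.3.2.2 says the estimand of the second supplementary analysis "will pursue a hypothetical strategy that estimates the effect of treatment in compliant subjects". Table 1 in SAP 3.2.1 lists it as "Compliant subjects hypothetical strategy". The endpoint and summary measure are those of the primary estimand. Two things change:

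- Population: "The population will consist of subjects that are at least 80% compliant with the drug regimen and complete the Week 48 visit".
- Intercurrent events: "subjects that discontinue treatment, or are lost to follow-up, before Week 48 are not included in the analysis".

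No imputation, weighting or model is given for what the excluded subjects' outcome would have been.

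The documents use the word *hypothetical* differently elsewhere. In SAP 6.3.2.1, study drop-out in the main analysis is handled "to estimate what the outcome would have been at the designated time point if all subjects were continued to be assessed". Protocol 9.4.2 describes its primary estimand as "estimating the effect of BHV-3241 relative to placebo had all subjects stayed on treatment", using the mITT population, on-treatment data and the MMRM. In both places the drop-outs stay in the analysis.

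SAP 6.2.6.1 derives compliance "by counting days where the number of tablets taken was > 0" and divides by the span from first to last dose.

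**The concern.** A hypothetical strategy asks what the Week 48 score would have been had the intercurrent event not occurred. Subjects with the event remain in the analysis, their earlier scores contribute, and the later ones are treated as missing. Supplementary Analysis 2 instead picks subjects by what happened to them after randomization, so the two groups are no longer protected by the randomization.

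The model cannot repair this. Every retained subject has a Week 48 visit, so the MMRM becomes in essence a covariate-adjusted Week 48 comparison. It has no Week 4 to Week 36 scores from drop-outs, and those scores give the main analysis its protection under MAR.

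At stake is how the result reads beside the primary. A contrast presented as the effect in compliant subjects could flatter or understate the drug. SAP 6.1.3 makes the multiple-imputation analyses conditional on significant results (SAP 6.3.2.3 does not repeat the condition), whereas Supplementary Analysis 2 carries no condition. After a non-significant primary result it could be one of the few alternative estimates reported.

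**Working it through.** **1. The plan's own figures (SAP 5.1).** Placebo change 4.88, SD 4.85, 40% improvement, two-sided alpha 0.05, power 90%.

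- Effect: 0.40 × 4.88 = 1.952 points.
- n per arm = 2 × (1.960 + 1.282)² × 4.85² / 1.952² = 129.7, so 130 per arm and 260 in total. Power from the noncentral t at 130 per arm is 0.898.
- 260 / 0.80 = 325 randomized, or 162.5 per arm.

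All the stated figures reproduce.

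**2. Completer bias in closed form.** Let a drop-out liability have correlation ρ with the Week 48 change, with fraction d dropping out. The completer mean then shifts by −ρ × SD × φ(z) / (1 − d), where z is the (1 − d) normal quantile. The documents give no value for ρ, so it is an assumption.

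At d = 0.20, z = 0.842 and φ(z) = 0.280, so the shift is −ρ × 4.85 × 0.350 = −1.697ρ. Bias below is for active minus placebo. Higher scores are worse, so a positive bias works against the drug. The standard error is 4.85 × √(2/130) = 0.60.

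| Drop-out active / placebo | ρ active / placebo | Bias (points) | % of 1.952 | Actual error of a nominal 5% test |
|---|---|---|---|---|
| 20% / 20% | 0 / 0 | 0.00 | 0 | 5.0% |
| 20% / 20% | 0.3 / 0.3 | 0.00 | 0 | 5.0% |
| 20% / 20% | 0 / 0.3 | +0.51 | 26 | 13.5% |
| 20% / 20% | 0.3 / 0 | −0.51 | 26 | 13.5% |
| 20% / 20% | 0 / 0.5 | +0.85 | 43 | 29.2% |
| 15% / 25% | 0.3 / 0.3 | +0.22 | 11 | 6.5% |

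The last row uses the completion seen in the earlier 12-week MSA study (protocol, Study D0490C00023): 17 of 20 on 600 mg and 15 of 20 on placebo. Those numbers are small, but the row shows that unequal rates with the same outcome link are enough to cause bias.

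**3. Does keeping the drop-outs remove it?** A two-visit simulation used 4,000 trials, 162 per arm, Week 48 SD 4.85, Week 24 SD 3.4 and correlation 0.7 between visits. Drop-out of 20% in each arm followed Week 24, with liability linked to the observed Week 24 score in one arm only.

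- Link 0.5: completer bias about 0.60; likelihood estimate using all data, 0.00.
- Link 0.7: completer bias about 0.83; likelihood estimate 0.00.
- Link 0.5 in both arms: both about 0.

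Step 2 agrees: 0.5 × 0.7 = 0.35 gives 1.697 × 0.35 = 0.59, and 0.7 × 0.7 = 0.49 gives 0.83.

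**4. Closer to the visit schedule.** A random-slope simulation had 162 per arm, SD about 4.83, no drug effect and assumed MAR drop-out of 11% to 29% per arm. When outcome-related drop-out differed by arm, it gave completer biases of about +0.50, −0.73 and −0.29 points. As shares of 1.952 these are 26%, 37% and 15%. The all-data likelihood estimate was off by 0.03 or less. With the same progression-driven drop-out in both arms, completer bias was about 0.

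On the step 2 scale, with 20% drop-out linked to outcome in one arm only, 0.29 to 0.73 points corresponds to ρ of 0.29 / 1.697 = 0.17 to 0.73 / 1.697 = 0.43.

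**5. Which condition does the excluding?** A day counts as compliant if any tablet was taken, and the denominator stops at the last dose. A subject who stops early can score 100%, as can one who takes a single tablet each day. The Week 48 condition therefore probably does most of the excluding.

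**The case against.** SAP 6.3.2.2 states its population and exclusions openly, so a reader can see a per-protocol analysis under a loose label. It is one of two supplementary analyses, it lies outside the gatekeeping, and no decision rests on it. That stands, and it limits the importance of the point.

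The size is also open to challenge. The likelihood estimate does well because drop-out was simulated as MAR. The simulations use raw completer means, whereas the planned model adjusts for baseline score, neurofilament and strata. Both are fair: the figures are illustrations, and the likelihood advantage depends on MAR.

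Three stronger readings are tempting and are not supported:

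- *Any difference between arms in drop-out reasons biases the analysis.* It does not. With equal progression-driven drop-out in both arms plus extra random drop-out on active (26% against 17% in total), a simulation gave a completer bias of +0.015 with Monte Carlo error 0.015.
- *Fast progressors stop more often in this disease.* Protocol 6.4 lists disease progression and adverse events among the reasons to stop. It gives no frequencies and no link to rate of decline.
- *Protocol 9.4.2 is contradicted here.* That section defines the primary estimand. It shows how the documents use the term but does not govern this supplementary analysis.

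A further objection is that censoring at discontinuation may nearly repeat the main MMRM. Subjects who stop get an Early Discontinuation visit and a Week 48 phone call for which no UMSARS is scheduled, so few off-treatment scores will exist. This is a real limit on what the fix adds.

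**Conclusion.** The mismatch between label and method holds whatever the drop-out pattern. Supplementary Analysis 2 selects on two post-randomization outcomes and does not estimate a hypothetical effect.

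Bias is conditional. It arises if outcome-related drop-out differs between arms in rate or strength, and the plausible size is about 0.3 to 0.7 points (15% to 37% of the planned effect) under the assumed patterns. Stronger assumed links give more, as the closed form shows. The direction is against the drug if progressors leave placebo more, and in its favour if they leave the active arm more. There is no bias if drop-out is unrelated to outcome or acts alike in both arms, and the documents do not show which case will apply.

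The primary test and type I error control are untouched. This is a worthwhile correction to a supplementary analysis and does not threaten the trial's conclusion.

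**What to change.** Redefine Supplementary Analysis 2 on the mITT set with the main MMRM. Use only efficacy data inside the double-blind on-treatment period of SAP 7.1, which for efficacy ends no later than last dose plus 7 days, and treat later scores as missing. This is the estimand protocol 9.4.2 describes. The SAP main analysis does not target it, because it handles drug discontinuation by treatment policy. Amend Table 1 to match.

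Do not add a rule that censors a subject once running compliance falls below 80%. The SAP defines one overall percentage per phase, and one missed day in the first four (3/4 = 75%) would remove every later score.

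If the compliant-completer set is also kept, call it a descriptive per-protocol completers summary and report no p-value. Relabelling alone would be honest but would leave the named effect unestimated.

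The cost is SAP wording and one further run of an existing model on a data period already defined. The downside is reliance on MAR after discontinuation, as the main model already has for study drop-out, and a result that may lie close to the main one.

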6.3.2.3 Sensitivity Analyses

For the primary endpoint, sensitivity analyses using multiple imputation (MI) will be conducted using a copy increment from reference and jump to reference approach to assess the impact of the MAR assumption of the analysis model used.

The primary analysis of the modified UMSARS score based on a MMRM model assumes that data is MAR and subjects who discontinue study medication prematurely have a response profile for the remainder of the treatment phase similar to subjects who completed the 48 weeks of the treatment phase (an analysis of a "de jure" or "hypothetical" based estimand). In order to explore the impact of these assumptions, a sensitivity analysis will be conducted where subjects who discontinue Verdiperstat prematurely have a response profile similar to those subjects on placebo using both a copy increment from reference and jump to reference approach. These analyses use a "defacto" estimand and are based on the methods described in.³

Mean changes from baseline in the modified UMSARS score will be analyzed based on data observed while the subject remains on study as well as data imputed using MI methodology for time points at which no value is observed. MI will be performed under the assumption of MAR and will be implemented in two steps. In the first step, a parameter-estimation model is fitted assuming MAR by a Markov chain Monte Carlo (MCMC) procedure in SAS with starting values based on fitting an MMRM model with the MIXED procedure. In the second step, an imputation model, which uses the parameters estimated in part 1, calculates predicted values for each pattern of withdrawal. Any intermediate missing values are imputed first assuming MAR, and then MNAR (missing not at random); part of the model is used to impute values for trailing missing values (e.g. after subject withdrawal from study). The MNAR part of the imputation will use a profile based on the estimated profile of the reference arm (placebo) to impute values after withdrawal for subjects in the Verdiperstat arm. In the case of the jump to reference approach, the mean response distribution after withdrawal will be used; and for the copy increment from reference, the mean increments will follow those from the placebo arm after withdrawal. Subjects in the placebo arm will use the profile under MAR.

For each analysis, the imputed data will consist of 1000 imputed data sets (using a MCMC length of 100). Both the parameter-estimation model and the imputation model will include fixed effect factors for treatment group, visit, and the treatment group by visit interaction. The baseline modified UMSARS score and visit by baseline interaction terms will be entered as covariates.

For each imputed dataset, the change from baseline for the modified UMSARS score at Week 48 will be based on observed and imputed data. An ANCOVA model will be used with baseline

modified UMSARS score and randomization strata (i.e., disease subtype, diagnostic category, and country) as covariates, and treatment groups will be compared at Week 48 based on LSM difference between Verdiperstat and placebo in each of the imputed data sets. Results from the analysis of each imputed dataset (LSM treatment differences and standard errors [SE]), will be combined using Rubin's imputation rules to produce a pooled LSM estimate of treatment difference, 95% CI, and a pooled p-value for the test of null hypothesis of no treatment effect.

An additional sensitivity analysis will be conducted on the primary endpoint using the same main analysis described in Section 6.3.2.1 but with a narrower visit window for Week 48 (See Section 7.2).

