6.1.4 Adjustments for Covariates and Stratification

The randomization was stratified by disease subtype (MSA-P vs. MSA-C), diagnostic category (possible MSA vs. probable MSA), and country. Hence, treatment group comparisons of continuous efficacy endpoints will be adjusted by disease subtype, diagnostic category, and country. If there are sparse data within a stratum, then stratum may be combined.

The analysis of the primary endpoint and other continuous efficacy endpoints will also be adjusted by the baseline value of the endpoint as a covariate in statistical models.

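### The reference-based imputation models omit the three randomization strata and baseline neurofilament, so the sensitivity result can differ from the main result for reasons other than the MAR assumption

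*SAP*

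**What the plan says.** SAP 6.3.2.3 describes a two-step multiple imputation, used once with jump-to-reference and once with copy increment from reference. Its purpose is "to assess the impact of the MAR assumption of the analysis model used".

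The terms of both steps are listed: "Both the parameter-estimation model and the imputation model will include fixed effect factors for treatment group, visit, and the treatment group by visit interaction". The next sentence completes the list: "The baseline modified UMSARS score and visit by baseline interaction terms will be entered as covariates". No stratum and no neurofilament term appears. For placebo drop-outs, "Subjects in the placebo arm will use the profile under MAR"; intermediate gaps are also filled under MAR.

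Each completed data set then goes to an ANCOVA that has the baseline "modified UMSARS score and randomization strata (i.e., disease subtype, diagnostic category, and country) as covariates".

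The primary MMRM in SAP 6.3.2.1 will "include fixed effect factors for treatment group, randomization strata (i.e., disease subtype, diagnostic category, and country), visit, and the treatment group by visit interaction". It has two continuous covariates: "Baseline modified UMSARS score and the baseline neurofilament level will enter the model as covariates".

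SAP 6.1.4 adds the general rule that "treatment group comparisons of continuous efficacy endpoints will be adjusted by disease subtype, diagnostic category, and country", and allows sparse strata to be combined.

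The key secondary endpoints use the methods of 6.3.2.3 if they are significant (SAP 6.3.3.1 to 6.3.3.4).

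**The concern.** A sensitivity analysis for MAR is informative when the missing-data assumption is the only thing that changes. Here the set of variables conditioned on changes too. The MMRM assumes MAR given strata, neurofilament, baseline and observed scores. The imputation assumes MAR for placebo drop-outs and for intermittent gaps without strata or neurofilament, and gives verdiperstat drop-outs a placebo profile estimated without them. The imputation model is also narrower than the ANCOVA that follows it.

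A gap between the MMRM and the imputed result then mixes two causes: the reference-based assumption and the reduced covariate set. In an unlucky pattern, the second could offset the first and make the result look more robust than it is. The reverse pattern would make it look more fragile.

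The analysis is likely to be run. The plan expects about 20% drop-out (SAP 5.1), and Protocol 9.4.6 calls for copy-increment imputation once more than 10% discontinue.

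**Working it through.** **Model terms side by side**

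| Term | Primary MMRM (6.3.2.1) | Both imputation steps (6.3.2.3) | ANCOVA after imputation (6.3.2.3) |
|---|---|---|---|
| Treatment | yes | yes | yes |
| Visit, treatment-by-visit | yes | yes | not applicable |
| Baseline score | yes | yes | yes |
| Visit-by-baseline | no | yes | not applicable |
| Subtype, diagnostic category, country | yes | **no** | yes |
| Baseline neurofilament | yes | **no** | **no** |

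**The plan's own figures (SAP 5.1).** The planned difference is 0.40 × 4.88 = 1.952 points, with SD 4.85. Per arm, n = 2 × (1.960 + 1.282)² × (4.85/1.952)² ≈ 129.7, so 130. Power at 130 per arm is 0.901 (normal approximation) or 0.898 (exact t-test). Then 260/0.80 = 325. All reproduce, and nothing below changes them.

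**Mechanism by hand (jump-to-reference).** Assume two equal strata lying +1 (worse) and −1 (better) around the mean, 20% drop-out overall, and no earlier visits to borrow from. Assume drop-out in the worse/better stratum of 10%/30% on placebo and 30%/10% on active.

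- Placebo completers average (0.9 − 0.7)/1.6 = +0.125. This value is imputed to all drop-outs.
- Placebo drop-outs should average (0.1 − 0.3)/0.4 = −0.5. Error in the arm mean: 0.2 × (0.125 + 0.5) = +0.125.
- Active drop-outs, on a stratum-specific placebo profile, should average (0.3 − 0.1)/0.4 = +0.5. Error: 0.2 × (0.125 − 0.5) = −0.075.
- Shift in the difference (active − placebo): −0.075 − 0.125 = **−0.20**.

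With 30%/10% in both arms, completers average −0.125 and drop-outs should average +0.5. Each arm's error is 0.2 × (−0.125 − 0.5) = −0.125, so the shift is **0**. For scale, the intended jump-to-reference penalty is about 0.2 × 1.952 = 0.39.

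**Simulation.** Inputs from the documents: N = 325, post-baseline visits at Weeks 4, 12, 24, 36 and 48, placebo change 4.88, SD 4.85, difference 1.952. Assumed, because the documents give no figures: 65% in one subtype, 75% in one diagnostic category, six countries with shares 40/15/15/10/10/10%, a combined stratum effect with SD of 0, 1 or 2 points at Week 48, and monotone drop-out of 19–22% whose log-odds change by 0, 0.5 or 1 per SD of that effect. Imputation used conditional means (the limit of many imputations), with and without strata, followed by the stratum-adjusted ANCOVA; 1,000 runs per row. The shift is the Week 48 difference without strata minus that with strata: mean (SD across trials).

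| Stratum SD | Log-odds; arms | Shift, jump-to-reference | Shift, copy-increment | Intended shift, jump / copy |
|---|---|---|---|---|
| 0 | 0 | 0.001 (0.031) | 0.001 (0.031) | +0.353 / +0.219 |
| 1 | 0 | −0.001 (0.047) | −0.001 (0.048) | +0.357 / +0.220 |
| 1 | 0.5; alike | 0.001 (0.046) | 0.001 (0.047) | +0.377 / +0.235 |
| 2 | 0.5; alike | 0.007 (0.073) | 0.009 (0.076) | +0.380 / +0.239 |
| 2 | 1; alike | 0.005 (0.081) | 0.006 (0.085) | +0.424 / +0.268 |
| 1 | 0.5; opposite | −0.113 (0.062) | −0.120 (0.064) | +0.378 / +0.237 |
| 2 | 0.5; opposite | −0.214 (0.086) | −0.227 (0.089) | +0.375 / +0.234 |
| 2 | 1; opposite | −0.439 (0.108) | −0.472 (0.112) | +0.424 / +0.268 |

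The intended shift is the reference-based result minus the MAR result, both with strata. The SD of the MAR treatment estimate was 0.52 to 0.61.

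In the three opposite-direction rows, the artefact is 0.113/0.378 = 30%, 57% and 104% of the intended jump-to-reference shift, and 51%, 97% and 176% of the copy-increment shift.

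**Limits.** The version with strata let their effects differ by visit; the SAP's MMRM has no such interaction. Neurofilament was not simulated, so no size is given for its omission.

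**The case against.** The strongest case is that little rides on this. Success is decided by the main MMRM (SAP 6.3.2.1 and 5.2). The imputation analyses carry no alpha, and SAP 6.1.3 runs them only after significant results. That stands as to stakes, although 6.3.2.3 states no such condition for the primary endpoint.

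A reader might infer four stronger things, none of which the documents support.

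- *That the sensitivity result is biased.* A systematic shift needs strata that predict outcome and stratum-related drop-out that differs by arm. The documents show neither. Protocol 1.2.1 says the two subtypes progress at the same rate on the UMSARS, which argues against the first condition for subtype; it is silent on diagnostic category, country and drop-out. A 2-point gap between strata would be 2/4.88 = 41% of the whole placebo change.
- *That every imputed subject gets an average over all strata.* The imputation also conditions on baseline and on the subject's earlier scores, which carry part of any stratum difference.
- *That SAP 6.1.4 is breached.* It governs treatment comparisons, and the comparison here is the ANCOVA, which is adjusted for strata.
- *That a shift computed under MAR imputation applies to these analyses.* It does not. MAR imputation gave −0.14 to −0.57 in the opposite-direction rows, larger than either reference-based method.

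It is also fair to object that adding strata alone would not make the comparison clean, because neurofilament and visit-by-baseline would still differ from the MMRM. That stands, and the fix is widened for it.

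**Conclusion.** The mismatch is in the text and is not an artefact of extraction or redaction: the imputation models omit three factors that their own ANCOVA and the primary MMRM include, and one MMRM covariate is absent from the whole sensitivity analysis. The sensitivity result can therefore move for reasons unrelated to MAR. It need not.

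If stratum-related drop-out is alike in both arms, the systematic shift is 0.01 points or less, with noise in a single trial of about 0.03 to 0.09 points. With prognostic strata and opposite drop-out by arm, the shift is about 0.1 to 0.5 points, comparable with the intended reference-based shifts of about 0.2 to 0.4. Those figures rest on assumed stratum effects, country shares and drop-out patterns. In the rows shown the shift favours verdiperstat; reversing the drop-out pattern reverses the sign.

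This is a free improvement to a pre-specified robustness analysis. The primary test and the sample size are untouched.

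**What to change.** In SAP 6.3.2.3:

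1. Add disease subtype, diagnostic category and country, pooled exactly as in the main MMRM, to both the parameter-estimation and the imputation model.
2. Add baseline neurofilament to both imputation steps and to the ANCOVA.
3. Run a MAR imputation with the same models and the same ANCOVA. The step from the MMRM to this bridge shows the effect of remaining model differences, including visit-by-baseline; the step from the bridge to jump-to-reference or copy-increment shows the reference-based assumption alone.
4. Apply the same rule to the key secondary imputation analyses, matching each endpoint's own MMRM covariates (baseline CGI-S for CGI-I).

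The cost is a few sentences and one extra imputation run. The strata are already used at randomization. Neurofilament is a measured value, so a rule for subjects without a baseline result should be stated. Pooling of sparse countries should be fixed before unblinding, so that all models use the same groups.
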